9.4. Data sources

This study will utilize data from IQVIA's PharMetrics® Plus. IQVIA's collaboration with Health Intelligence Company, which operates as Blue Health Intelligence, allows IQVIA's bio-pharmaceutical clients sole access to one of the largest United States (US) health plan claims databases and adds IQVIA's market leading health plan claims database. The aggregated database comprises adjudicated claims for more than 190 million unique enrollees across the US. Enrollees with both medical and pharmacy coverage in 2020 represented 40 million lives. Data are available from 2010 onwards, with a typical 4- to 6-month lag due to claims adjudication.

PharMetrics Plus has diverse representation of geography, employers, payers, providers and therapy areas. Patients in each zip code and every Metropolitan Statistical Area of the US are included, with coverage of data from 90% of US hospitals, 80% of all US doctors, and representation from 85% of the Fortune 100 companies. In addition to standard fields such as inpatient and outpatient diagnosis and procedures, retail and mail-order prescription records, PharMetrics Plus has detailed information on the pharmacy and medical benefit (copayment, deductible), the inpatient stay (admission type and source, discharge status) and provider details (specialty, provider identifier [ID]). All zip codes in the US are covered and reported allowing more granular patient segmentation and comparisons by geography. Payment amounts include the negotiated rate between the plan and providers (allowed) and the actual amount paid by health plans to the provider for all services rendered. Charge amount is also available for a subset of claims. Other data elements include dates of service, demographic

PFIZER CONFIDENTIAL

CT24-WI-GL02-RF02 4.0 Non-Interventional Study Protocol Template For Secondary Data Collection Study 01-Jun-2022

Page 27 of 35

090177e19b7d94e0\Approved\Approved On: 29-Aug-2023 01:40 (GMT)

Apixaban

B0661183 NON-INTERVENTIONAL STUDY PROTOCOL

Protocol Version: 2.0 29 July 2022

variables (age, gender, and geographic region), product type (e.g., HMO, PPO), payer type (e.g., commercial, self-insured), and start and stop dates of health-plan enrollment.

Due to the broad reach of the data, records in PharMetrics Plus are representative of the national, commercially insured population in terms of age and gender for individuals aged 65 and under. The data are also longitudinal, with more than 20 million patients who have both medical and pharmacy coverage with 3 or more years of continuous enrollment. Data contributions are subjected to a series of quality checks to ensure a standardized format and to minimize error rates. All data are Health Insurance Portability and Accountability Act (HIPAA)-compliant to protect patient privacy.

PharMetrics Plus will be largely commercially- or self-insured and may not be representative of un-insured or Medicare or Medicaid populations. Further research will be warranted to understand the costs of patient archetypes among these other populations, particularly those aged 65+ and covered by traditional fee-for-service Medicare. Additionally, there is a lack of visibility into HCRU or prescriptions obtained outside of the plan benefit.

9.5. Study size

An earlier feasibility study estimated that there were 4,972 VTE patients with cancer with evidence of apixaban in PharMetrics® Plus. These counts were for informational purposes only and will not represent the actual number of patients to be utilized in the study. Application of other inclusion and exclusion criteria or other factors will reduce the sample size.

Sample size calculation was conducted to identify minimum number of patients in each cohort required for the analysis using the recurrent VTE event rates from Cohen et al.^{Error! Bookmark not defined.} and Agnelli et al.^{Error! Bookmark not defined.} to achieve a power of 80% at a 5% level of significance (two-sided). Using recurrent VTE rates 4.362% (148 recurrent VTE cases in 3,393 patients) in apixaban cohort and 6.483% (396 recurrent VTE cases in 6,108 patients) in LMWH cohort from Cohen et al., we require a minimum sample of 1,788 patients in each cohort to achieve 80% power. A minimum sample of 1,867 patients in each cohort is required to achieve 80% power at a 5% level of significance (two-sided) using recurrent VTE event rates from Agnelli et al. of 5.6% in apixaban cohort and 7.9% in dalteparin cohort. Based on the sample size calculations, for the current study we need a minimum sample in the range of 1,788-1,867 patients in each cohort.

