Descriptive statistics will be produced for all relevant study measures, for the 2 therapy cohorts. Stabilized inverse probability treatment weighting (IPTW) will be used to balance patient characteristics between apixaban and LMWH cohorts. Post-IPTW, comparisons will be conducted using weighted chi-square tests for categorical variables and weighted t-tests (mean) for continuous variables. Comparisons between independent samples (e.g., among patients with ≥ 1 hospitalization) and pre-IPTW samples will be conducted using the parametric t-test (mean) and non-parametric Wilcoxon rank-sum test (median) for continuous variables. A p value of ≤ 0.05 will be considered significant.

Up to 4 regression models will be developed and these may include weighted generalized linear models (GLM) with log transformation and gamma distribution to estimate adjusted (all-cause) cost ratio between the two cohorts or a negative binomial distribution may be developed to estimate adjusted visits such as physician office visits, emergency room visits or other HCRU.

Milestones

Protocol and table shells: 12 August 2022

Start of data analysis: 15 August 2022

PFIZER CONFIDENTIAL

CT24-WI-GL02-RF02 4.0 Non-Interventional Study Protocol Template For Secondary Data Collection Study 01-Jun-2022

Page 10 of 35

090177e19b7d94e0\Approved\Approved On: 29-Aug-2023 01:40 (GMT)

Apixaban

B0661183 NON-INTERVENTIONAL STUDY PROTOCOL

Protocol Version: 2.0 29 July 2022

Final results: 21 October 2022

Final study reports and presentation: 18 November 2022

090177e19b7d94e0\Approved\Approved On: 29-Aug-2023 01:40 (GMT)

PFIZER CONFIDENTIAL

CT24-WI-GL02-RF02 4.0 Non-Interventional Study Protocol Template For Secondary Data Collection Study 01-Jun-2022

Page 11 of 35

Apixaban
B0661183 NON-INTERVENTIONAL STUDY PROTOCOL
Protocol Version: 2.0 29 July 2022

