8. RESEARCH QUESTION AND OBJECTIVES

The purpose of this study is to evaluate the costs and HCRU associated with treating VTE cancer patients with apixaban compared to LMWH (dalteparin, enoxaparin, or tinzaparin).

The objectives of the study are as follows:

Primary objectives:

- To compare all-cause healthcare costs among VTE patients with cancer treated with apixaban vs LMWH
- To compare costs associated with recurrent VTE, major bleeding, and clinically relevant non-major (CRNM) bleeding among VTE patients with cancer treated with apixaban vs LMWH

Secondary objectives:

- To compare all-cause HCRU among VTE patients with cancer treated with apixaban vs LMWH
- To compare HCRU associated with recurrent VTE, major bleeding, and CRNM bleeding among VTE patients with cancer treated with apixaban vs LMWH

090177e19b7d94e0\Approved\Approved On: 29-Aug-2023 01:40 (GMT)

PFIZER CONFIDENTIAL

CT24-WI-GL02-RF02 4.0 Non-Interventional Study Protocol Template For Secondary Data Collection Study 01-Jun-2022

Page 15 of 35

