9.7. Data analysis

Descriptive statistics will be produced for all relevant study measures previously described, for the 2 therapy cohorts of interest. Categorical measures will be presented using frequency (number of patients [n]) and percentage (%) of total study patients observed in each category. Continuous and count variables will be presented as the mean, SD, median and IQR. As relevant, continuous variables will also be categorized into intervals.

Stabilized IPTW will be used to balance patient characteristics between apixaban and LMWH cohorts.^{11,12} Weights will be constructed by estimating each subject's probability of receiving treatment based on covariates. For comparisons of baseline characteristics between the apixaban and LMWH cohorts, both pre- and post-IPTW, standardized mean difference (SMD) will be calculated to evaluate the difference in baseline covariates between cohorts. SMD is calculated as the difference in means or proportions of a variable divided by the pooled standard deviation. SMD of ≥ 0.10 between groups is considered meaningful.¹³ For comparisons of events and HCRU/cost over the variable post-index period post-IPTW, comparisons will be conducted using weighted chi-square tests for categorical variables and weighted t-tests (mean) for continuous variables (note there is no corresponding weighted test for the median). Comparisons between independent samples (e.g., among patients with ≥ 1 hospitalization) and pre-IPTW samples will be conducted using the parametric t-test (mean) and non-parametric Wilcoxon rank-sum test (median) for continuous variables; data will be reported for the unweighted sample. A p-value < 0.05 will be considered statistically significant. However, to account for multiple comparisons, a Bonferroni correction may be implemented such that the critical p-value ($p < .05$) may be divided by the number of comparisons (i.e., 3 comparisons, in order to yield a new critical p-value, $.05/3 = 0.0167$). Analyses will be conducted using SAS[®] (statistical analysis software) Release 9.4 (SAS Institute Inc., Cary, NC).

IQVIA will develop up to 4 multivariable analysis models, to be mutually agreed upon Pfizer/BMS and IQVIA. For example these may include weighted generalized linear models (GLM) with log transformation and gamma distribution to estimate adjusted (all-cause) cost ratio

PFIZER CONFIDENTIAL

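### The stated 80% power covers only an unweighted test of recurrent VTE occurrence at 0.05, while the four primary cost comparisons lack a matching power statement and a fixed significance rule

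*Combined protocol and SAP*

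**What the plan says.** Section 9.5 bases the calculation on one quantity; the minimum number per cohort is that "required for the analysis using the recurrent VTE event rates from" two published studies. The claims-based scenario uses "4.362% (148 recurrent VTE cases in 3,393 patients) in apixaban cohort" and "6.483% (396 recurrent VTE cases in 6,108 patients) in LMWH cohort", giving 1,788 per cohort. The scenario from the cited randomised trial uses 5.6% and 7.9%, giving 1,867. Both are for 80% power at two-sided 5%, and the section concludes that "for the current study we need a minimum sample in the range of 1,788-1,867 patients in each cohort". It also reports a feasibility count of 4,972 apixaban patients, says that further criteria will reduce it, and gives no LMWH count.

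Section 8 has two primary objectives. The first is "To compare all-cause healthcare costs among VTE patients with cancer treated with apixaban vs LMWH". The second is to compare costs associated with recurrent VTE, major bleeding and CRNM bleeding. Together they name four costs.

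Section 9.7 tests post-index outcomes on weighted data and takes p < 0.05 as significant. It then says that a Bonferroni correction is possible, in which the critical value "may be divided by the number of comparisons (i.e., 3 comparisons, in order to yield a new critical p-value" of 0.0167. It does not name the three comparisons or say what would trigger the correction. The abstract says only: "A p value of ≤ 0.05 will be considered significant".

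**The concern.** A reader of Section 9.5 will take 80% power at 5% as describing the main analysis. It describes a different quantity (whether a recurrent VTE occurs), a different analysis (unweighted), and possibly a different threshold (0.05, where 0.0167 may apply). Nothing in the plan says how large a difference in all-cause cost the study could detect.

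The significance rule is also open. Section 12 has result tables going to the sponsor throughout the analytic phase, so the choice between 0.05 and 0.0167 could be made after p-values are known. A primary cost result with p between those values could then be called significant or not, and either call would comply with the protocol. The promise in Section 9.7 to amend for major changes to primary endpoints or their analyses does not clearly close this gap, because using or skipping an option already in the text changes nothing.

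**Working it through.** **1. Reproduce the stated sample sizes.** Inputs are the rates in Section 9.5, two-sided alpha 0.05, 80% power and equal cohorts. The pooled two-proportion formula without continuity correction is

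n = [z(1−α/2)·√(2p̄(1−p̄)) + z(0.80)·√(p1(1−p1)+p2(1−p2))]² / (p2−p1)²

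- Claims rates (148/3,393 and 396/6,108): p̄ = 0.05423, difference 0.02121. n = [(1.960 × 0.3203 + 0.8416 × 0.3199)/0.02121]² = 1,787.8, so 1,788.
- Trial rates (0.056 and 0.079): p̄ = 0.0675, difference 0.023. n = [(1.960 × 0.3548 + 0.8416 × 0.3544)/0.023]² = 1,866.6, so 1,867.

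Both figures are correct for that test.

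**2. Same endpoint and n, at the plan's optional level.** At α = 0.05/3, z = 2.394. Power = Φ{[(p2−p1)√n − z·√(2p̄(1−p̄))] / √(p1(1−p1)+p2(1−p2))}.

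- Claims rates, n = 1,788: (0.8970 − 2.394 × 0.3203)/0.3199 = 0.407, power 65.8%.
- Trial rates, n = 1,867: (0.9938 − 2.394 × 0.3548)/0.3544 = 0.407, power 65.8%.
- For 80% power the same formula, rounded up, needs 2,385 (claims) or 2,491 (trial) per cohort.
- At 0.05/4 = 0.0125, power is 61.9% in both scenarios.

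**3. Familywise error for the four named costs.**

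- Uncorrected: 1 − 0.95⁴ = 18.5% if independent.
- All four at 0.05/3: 1 − (1 − 0.0167)⁴ = 6.5% if independent; the Bonferroni bound is 4 × 0.05/3 = 6.7%.

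The four costs overlap, since event costs are part of all-cause cost. The independent figures therefore illustrate the size and do not estimate it.

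**4. Weighting.** The plan gives no design effect, so these values are assumed and n is divided by each. Power for recurrent VTE occurrence at the stated n:

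| Assumed design effect | α = 0.05 | α = 0.05/3 |
|---|---|---|
| 1.1 | 76% | 61% |
| 1.25 | 71% | 54% |
| 1.5 | 63% | 46% |

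**5. What a cost statement could look like.** The plan gives no cost SD, so a coefficient of variation (CV) of 1.5 to 2.5 is assumed. With 1,867 per cohort, α = 0.05 and 80% power, the detectable ratio of mean costs is about exp(2.80 × CV × √(2·D/1,867)), where D is the design effect.

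- D = 1: exp(2.80 × 1.5 × 0.0327) = 1.15, up to exp(2.80 × 2.5 × 0.0327) = 1.26.
- D = 1.25 (assumed): 1.17 to 1.29.

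**The case against.** **The sizing is not irrelevant to the primary objectives.** Under Section 9.3.3, recurrent VTE-related cost starts with the first recurrent VTE hospitalisation, so it should be positive only in patients with that event. Section 9.7 analyses event-related costs with a two-part model whose first part is the probability of a positive cost. Apart from weighting and covariate adjustment, that is close to the proportion sized in Section 9.5. This stands. The gap is limited to the other three costs and to the amount of cost among patients with events.

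**A reader might infer that the primary cost analysis has 66% power.** The documents do not support that. The 65.8% is for recurrent VTE occurrence at the minimum n; power for any cost cannot be computed without a cost SD.

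**A reader might also infer that dividing by three is an error for four.** Section 9.7 never says which three comparisons it means, and the second primary objective lists exactly three event costs, which would fit. On that reading, all-cause cost is outside the correction. What can be shown is that the family is undefined.

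**The study may be large enough anyway.** This is an existing database, 1,788 to 1,867 is a floor, and 4,972 is about twice 2,491. That is fair, but the count will fall and the LMWH cohort size is not stated.

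**Conclusion.** The point holds in limited form. The sample-size arithmetic is correct; the faults are its scope and the unfixed significance rule. The 80% applies to unweighted recurrent VTE occurrence at 0.05. On the same endpoint and n it becomes 65.8% at the plan's own 0.0167, before any loss from weighting. Three of the four primary costs, and the amount of cost among patients with events, have no power or precision statement.

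As written, the plan permits four primary tests at 0.05, with familywise error of 18.5% if they are independent, or a threshold chosen after tables have been seen. This affects what may be reported as significant, so it is more than missing detail.

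The 65.8%, 2,385 and 2,491 follow from the documents alone. The design effects and CVs are assumptions, and the count of four is read from the objectives. A conclusion that the study will be underpowered would go too far: the documents establish neither adequacy nor shortfall.

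**What to change.** 1. **Sections 9.7 and 4 (abstract).** Replace the optional correction with one mandatory rule that names its comparisons, worded identically in both places. One option is to test all-cause cost first at 0.05 and, only if it is significant, the three event-related costs at 0.0167 each. This holds familywise error at 5% and gives the divisor of three a clear meaning. The plan does not rank its two primary objectives, so Bonferroni at 0.05/4 = 0.0125 across all four is equally valid.
2. **Section 9.5.** Label 1,788 to 1,867 as unweighted, alpha 0.05, recurrent VTE occurrence only, and state the 65.8% at 0.0167. Add the detectable all-cause cost ratio at the effective sample size achieved after weighting, over a stated CV range; step 5 of the working shows the form.

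The cost is wording in three places and a less favourable power statement. No more patients are needed.

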9.6. Data management

See sections 8.4 and 8.7.

9.6.1. Case report forms (CRFs)/Data collection tools (DCTs)/Electronic data record

Not applicable.

9.6.2. Record retention

To enable evaluations and/or inspections/audits from regulatory authorities or Pfizer, IQVIA agrees to keep all study-related records, including study documentation, archived analytic

PFIZER CONFIDENTIAL

CT24-WI-GL02-RF02 4.0 Non-Interventional Study Protocol Template For Secondary Data Collection Study 01-Jun-2022

Page 28 of 35

090177e19b7d94e0\Approved\Approved On: 29-Aug-2023 01:40 (GMT)

Apixaban

B0661183 NON-INTERVENTIONAL STUDY PROTOCOL

Protocol Version: 2.0 29 July 2022

datasets, and adequate documentation of relevant correspondence. The records should be retained by IQVIA according to local regulations or as specified in the study protocol, whichever is longer. IQVIA must ensure that the records continue to be stored securely for so long as they are retained.

If IQVIA becomes unable for any reason to continue to retain study records for the required period, Pfizer should be prospectively notified. The study records must be transferred to a designee acceptable to Pfizer.

Study records must be kept for a minimum of 15 years after completion or discontinuation of the study, unless IQVIA and Pfizer have expressly agreed to a different period of retention via a separate written agreement. Record must be retained for longer than 15 years or as required by applicable local regulations.

IQVIA must obtain Pfizer's written permission before disposing of any records, even if retention requirements have been met.

9.7. Data analysis

Descriptive statistics will be produced for all relevant study measures previously described, for the 2 therapy cohorts of interest. Categorical measures will be presented using frequency (number of patients [n]) and percentage (%) of total study patients observed in each category. Continuous and count variables will be presented as the mean, SD, median and IQR. As relevant, continuous variables will also be categorized into intervals.

Stabilized IPTW will be used to balance patient characteristics between apixaban and LMWH cohorts.^{11,12} Weights will be constructed by estimating each subject's probability of receiving treatment based on covariates. For comparisons of baseline characteristics between the apixaban and LMWH cohorts, both pre- and post-IPTW, standardized mean difference (SMD) will be calculated to evaluate the difference in baseline covariates between cohorts. SMD is calculated as the difference in means or proportions of a variable divided by the pooled standard deviation. SMD of ≥ 0.10 between groups is considered meaningful.¹³ For comparisons of events and HCRU/cost over the variable post-index period post-IPTW, comparisons will be conducted using weighted chi-square tests for categorical variables and weighted t-tests (mean) for continuous variables (note there is no corresponding weighted test for the median). Comparisons between independent samples (e.g., among patients with ≥ 1 hospitalization) and pre-IPTW samples will be conducted using the parametric t-test (mean) and non-parametric Wilcoxon rank-sum test (median) for continuous variables; data will be reported for the unweighted sample. A p-value < 0.05 will be considered statistically significant. However, to account for multiple comparisons, a Bonferroni correction may be implemented such that the critical p-value ($p < .05$) may be divided by the number of comparisons (i.e., 3 comparisons, in order to yield a new critical p-value, $.05/3 = 0.0167$). Analyses will be conducted using SAS[®] (statistical analysis software) Release 9.4 (SAS Institute Inc., Cary, NC).

IQVIA will develop up to 4 multivariable analysis models, to be mutually agreed upon Pfizer/BMS and IQVIA. For example these may include weighted generalized linear models (GLM) with log transformation and gamma distribution to estimate adjusted (all-cause) cost ratio

PFIZER CONFIDENTIAL

CT24-WI-GL02-RF02 4.0 Non-Interventional Study Protocol Template For Secondary Data Collection Study 01-Jun-2022

Page 29 of 35

090177e19b7d94e0\Approved\Approved On: 29-Aug-2023 01:40 (GMT)

Apixaban

B0661183 NON-INTERVENTIONAL STUDY PROTOCOL

Protocol Version: 2.0 29 July 2022

between the two cohorts. A negative binomial distribution may be developed to estimate adjusted visits such as physician office visits, emergency room visits or other HCRU. Two-part regression analyses will be used to evaluate the impact of the LMWH treatments relative to apixaban on recurrent VTE-related, major bleeding-related, CRNM-related medical HCRU or costs. The 2-part regression analyses¹⁴ will be used to avoid the analytical issues associated with the large number of data with 0 values for HCRU and costs for VTE-related, major bleeding-related, CRNM related HCRU and costs. In the two-part model, first the probability of observing a positive versus zero outcome will be determined using a binary choice model. In the second part of the model, conditional on a positive outcome, an appropriate regression model such as a GLM model for costs or a negative binomial model for HCRU will be fit for the positive outcome. Covariates to be considered for inclusion into the models will include demographic and clinical characteristics of interest guided by the univariate findings. These candidate variables will be considered and retained in the model if significant ($SMD \geq 0.10$) using a stepwise approach. Collinearity among the variables of interest will be evaluated during model development.

Any major modifications of primary endpoint definitions or their analyses would be reflected in a protocol amendment.

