9.3.2. All-cause HCRU and Costs Over the Post-Index Period (Post-IPTW)

All-cause HCRU and costs will be reported for the Apixaban and LMWH cohorts over the variable post-index period (minimum 1 month enrollment), post-IPTW. Costs will be reported

PFIZER CONFIDENTIAL

CT24-WI-GL02-RF02 4.0 Non-Interventional Study Protocol Template For Secondary Data Collection Study 01-Jun-2022

Page 23 of 35

090177e19b7d94e0\Approved\Approved On: 29-Aug-2023 01:40 (GMT)

Apixaban

B0661183 NON-INTERVENTIONAL STUDY PROTOCOL

Protocol Version: 2.0 29 July 2022

as per patient per month (PPPM). Over the post-index period, a 30 day period will be used (to represent a month) to ‘standardize’ the period of time for which costs and HCRU will be reported. For each patient, costs will be divided by the variable post-index period in total-person days and then multiplied by 30 to calculate PPPM costs. For example, if a patient has total costs of \$10,000 with 60 days of follow-up, the PPPM will be calculated as $(\$10,000/60) * 30 = \$5,000$.

HCRU will be expressed as both the proportion of patients with such utilization (e.g., the percentage of patients with at least one pharmacy claim, the percentage of patients with at least one physician office visits, etc.) as well as per-patient mean, SD, median and IQR number of visits/services. Costs will be expressed as per-patient mean, SD, median and IQR. Utilization and costs will be calculated on a per patient basis, averaged across the cohort. The denominator will include all patients in the cohort. Costs will be converted to 2021 US dollars (USD) using the medical component of the Consumer Price Index.

HCRU and costs will be reported for mutually exclusive categories: outpatient pharmacy, inpatient hospitalizations, and outpatient care. Outpatient care will comprise the following categories: ER visits, outpatient physician office visits, outpatient surgical visits, laboratory and pathology, radiology and all other services.

All-cause HCRU and costs will be reported for each of the following services:

- Pharmacy
 - Patients with ≥ 1 prescription fill (n, %)
 - Number of prescription fills per patient (mean, SD, median, IQR)
 - Total pharmacy cost per patient (mean, SD, median, IQR)
- Outpatient Services
 - Total outpatient medical care cost per patient (mean, SD, median, IQR)
 - Physician office visits
 - Patients with ≥ 1 physician office visit (n, %)
 - Number of physician office visits per patient (mean, SD, median, IQR)

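### Percentages with at least one event or visit, and the any-versus-none part of the two-part models, take no account of on-treatment follow-up that may differ between cohorts

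*Combined protocol and SAP*

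**What the plan says.** Sections 9.1 and 9.1.1 (item 5) define follow-up as variable, with a one-month minimum. It stops at the earliest of disenrollment, discontinuation of the index drug, switch to another anticoagulant, or study end.

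Section 9.3.2 states that "HCRU will be expressed as both the proportion of patients with such utilization", together with counts per patient, over all patients in the cohort. It divides costs by follow-up days and multiplies by 30 (PPPM). It says the 30-day period standardises HCRU too, but gives a formula only for costs. Section 9.3.3 asks for the number and percentage of patients with at least one recurrent VTE, major bleed or CRNM bleed. It also asks for the mean, median, SD and IQR of time to first event, and names no method for censoring.

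Section 9.7 says that for events, HCRU and costs over the variable post-index period "comparisons will be conducted using weighted chi-square tests for categorical variables and weighted t-tests (mean) for continuous variables". In the two-part models for event-related HCRU and costs, "first the probability of observing a positive versus zero outcome will be determined using a binary choice model"; then, among positive outcomes, a GLM is suggested for costs, while "a negative binomial model for HCRU will be fit for the positive outcome". No offset, exposure term or fixed window is stated.

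Section 9.5 sizes the study on crude recurrent VTE proportions: "4.362% (148 recurrent VTE cases in 3,393 patients) in apixaban cohort and 6.483% (396 recurrent VTE cases in 6,108 patients) in LMWH cohort" from a claims study and "5.6% in apixaban cohort and 7.9% in dalteparin cohort" from a randomised trial. It concludes that "we need a minimum sample in the range of 1,788-1,867 patients in each cohort".

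**The concern.** The chance of at least one event or visit rises with time observed. Because observation stops when the index drug stops, a cohort that stays on drug longer will show a higher percentage with an event even if the risk per month is the same. The chi-square test and the first-part odds ratio would then reflect persistence as well as risk.

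Nothing stated in the plan corrects this. Dividing by days cannot standardise a percentage with at least one event. Stabilized IPTW balances patient characteristics, not time on drug after index. Means and medians of time to first event, taken among patients who had one, also depend on how long each cohort was watched.

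At stake are the event and any-use comparisons, the quantity on which the sample size rests, and the first part of the models for event-related costs, which belong to a primary objective.

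**Working it through.** **1. The plan's own figure.** Inputs from section 9.5: two-sided 5%, 80% power, equal cohorts. The pooled-variance formula for two proportions, without continuity correction, is

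n = [1.96·√(2p̄(1−p̄)) + 0.8416·√(p₁(1−p₁)+p₂(1−p₂))]² / (p₁−p₂)².

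- 4.362% vs 6.483%: n = 1,788.4 (1,787.8 with the exact fractions 148/3,393 and 396/6,108). The plan says 1,788.
- 5.6% vs 7.9%: n = 1,866.6. The plan says 1,867.

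Both reproduce. The calculation compares crude proportions and has no term for a follow-up difference.

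**2. Equal risk, unequal follow-up.** Take LMWH at 6.483% and the same constant hazard in both cohorts. Let r be the ratio of apixaban to LMWH follow-up (assumed). The cumulative hazard is H = −ln(1−0.06483) = 0.0670, and the apixaban proportion is p = 1 − exp(−H·r). The rejection rate uses the test in step 1 at 1,788 per cohort and ignores the effect of weighting on variance.

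| r | Apixaban % | LMWH % | First-part odds ratio | Rejects at 5% |
|---|---|---|---|---|
| 1 | 6.5 | 6.5 | 1.00 | 5% |
| 1.25 | 8.0 | 6.5 | 1.26 | 43% |
| 1.5 | 9.6 | 6.5 | 1.53 | 92% |
| 2 | 12.6 | 6.5 | 2.07 | >99.9% |

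The correct odds ratio is 1 in every row. If LMWH patients stay on drug longer, the bias runs the other way.

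**3. A real difference can disappear.** Suppose the planned 4.362% vs 6.483% holds at equal follow-up. The hazard ratio is 0.0446/0.0670 = 0.665. With r = 1.5 the apixaban proportion is 1 − exp(−0.0446×1.5) = 6.47%, against 6.48%, so rejection falls from 80% to the 5% false-positive level. With r = 2 it is 8.5% against 6.5%, and the direction reverses.

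**4. Does a rate comparison cure it?** Simulation: 4,000 runs, 1,788 per cohort, follow-up of one month plus an exponential time, equal hazard of 2% per month (assumed).

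| Mean follow-up, LMWH vs apixaban (months) | Chi-square rejects | Person-time rate test rejects |
|---|---|---|
| 3 vs 3 | 5% | 5.3% |
| 3 vs 4 | 57% | 4.5% |
| 3 vs 4.5 | 87% | 4.6% |
| 3 vs 6 | >99.9% | 4.9% |

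With a true rate ratio of 0.67 and 3 vs 4.5 months, the chi-square rejects in 5% of runs and the rate test in 82%.

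**5. The combined cost estimate.** Mean PPPM cost = P(cost > 0) × E(PPPM cost | cost > 0). Longer follow-up raises the first factor and lowers the second. At 1% per month, 3 vs 6 months, equal risk and a fixed cost per event, the first-part ratio is 1.94, the second-part ratio 0.52, and the product 1.94 × 0.52 ≈ 1.0. Section 9.3.3 also counts all later event-related medical costs after the first event, and these grow with follow-up. If they run at 15% of the event cost per month (assumed), the combined ratio at 3 vs 6 months is about 1.15 to 1.17, depending on the simulation set-up.

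**The case against.** **The documents do not say that follow-up will differ, or in which direction.** This stands. Every size above is conditional on an assumed ratio, and no cohort is presumed to be followed longer.

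**Follow-up duration could enter the models.** Section 9.3.1 lists it under demographic characteristics, and section 9.7 makes those candidate covariates, kept when the SMD is at least 0.10. This is possible, but it is not a prespecified exposure adjustment and does nothing for the chi-square tests.

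**A reader might infer that the primary cost results are biased.** The documents do not support that. All-cause costs are PPPM. Section 9.3.3 carries the section 9.3.2 cost variables over to event-related costs (its cross-reference reads 8.3.2), and on that reading the two parts largely offset, as step 5 shows. What remains is the first part read alone, and the accumulation of later event costs. The plan does not say whether the two parts will be combined.

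**A reader might also infer that an untruncated negative binomial fitted to counts of one or more gives a wrong effect size.** It does not. For a Poisson count with mean 0.35 and a true rate ratio of 1.5, the any-use ratio is 0.408/0.295 = 1.383 and the true ratio of conditional means is 1.285/1.185 = 1.085; 1.383 × 1.085 = 1.50. Only the standard errors suffer. They are too large, by about √(1.185/0.195) = 2.46 in this example, and only if raw counts and model-based errors are used. HCRU is a secondary objective, and the plan offers the negative binomial as an example.

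**Rate methods bring their own assumption,** that stopping or switching is unrelated to event risk. This stands and calls for a sensitivity analysis.

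**Conclusion.** The point holds for the tested percentages with at least one event or visit, for the first-part effect of the two-part models read alone, and for the summaries of time to first event. If time on drug differs between cohorts, these measure persistence together with risk.

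Under a constant and equal hazard, the plan's 6.483% and 1,788 per cohort, a follow-up ratio of 1.25 already gives 43% false rejection, and a ratio of 1.5 gives 92%. At a ratio of 1.5 the planned recurrent VTE contrast would vanish. If follow-up proves equal, the distortion is nil.

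The point does not reach all-cause PPPM cost means. It reaches combined event-related PPPM costs only to the extent that later event costs accumulate. No stated objective is event incidence itself. For these reasons it should be fixed, but it does not undermine the primary cost comparison.

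**What to change.** - Compare events and visits by weighted rates: Poisson or negative binomial on raw counts, with log(follow-up days) as offset and robust errors. Weighted Kaplan-Meier or Cox analysis is an alternative, and should in any case replace the simple summaries of time to first event.
- In the first part of the two-part models, use a complementary log-log link with a log(follow-up days) offset.
- Report the combined two-part PPPM cost difference, with bootstrap or robust intervals, as the event-related cost result. Do not interpret the parts separately.
- Keep crude percentages as description, without p-values, beside follow-up time by cohort.
- Add a sensitivity analysis for informative censoring at discontinuation or switch.
- State whether HCRU counts are raw or scaled to 30 days. If raw positive counts are modelled, use a zero-truncated negative binomial or robust errors, for correct standard errors only.

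Cost: revised wording in section 9.7 and modest extra programming. Follow-up days are already needed for PPPM, so no new data are required. The price is an assumption of a roughly constant rate over follow-up for the offset models.
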